7.8.2.2. Clinical Significance

Clinical significance is defined by how a treatment affects the extent to which a subject is currently living independent of help from others OR that there is a real genuine, palpable, and noticeable effect on daily life or how a patient feels, functions, or survives. Importantly, as the scores from the MDS-NMS are derived from the product of the symptom frequency (how often the patient has experienced a given non-motor symptom since the last evaluation with higher scores indicating more frequent experience) and symptom severity (impact of that symptom on how the patient has felt and functioned with higher scores indicating greater distress or disturbance to patient or caregiver), reductions in MDS-NMS total scores are inherently clinically meaningful in that they indicate improvements in how the participant is feeling and functioning. Given the inherent clinical meaningfulness of the MDS-NMS total score, the primary endpoint will be considered clinically meaningful, and therefore, successful, if there are statistically significant reductions in MDS-NMS total scores after active tvCVS treatment during the OLE relative to the change in response to the 12 weeks of passive treatment during the RCT.

7.8.2.2.1. Supportive Analysis: Clinical Significance

Data collected during the RCT will be used to define a Minimally Important Clinical Difference (MCID) in the primary outcome measure (the MDS-NMS).

Supportive analyses will also be conducted on the data from the OLE to determine whether the difference in the change scores between the active treatment in the OLE and the passive treatment during the RCT exceeds the MCID defined for the MDS-NMS in the RCT. This test will be based on the MMRM model described in Section 7.7 of the RCT SAP (Appendix 1), comparing the least-squares mean change of the active treatment (as estimated by the model) to the point estimate of the MCID determined from the RCT.

7.8.3. Secondary Objectives:

This study will seek to further evaluate the effectiveness of TNMTM treatments to provide adjuvant therapeutic effectiveness beyond that observed with DRTs to (1) provide global improvements related to PD symptoms, (2) improve activities of daily living related to motor function, (3) provide clinically meaningful change (4) improve motor symptoms and (5) improve quality of life (QoL) for participants with PD, for the purposes of supporting reimbursement and clinical adoption.

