7.8.2. Primary Endpoint and Comparison of Interest

The primary endpoint is the change in MDS-NMS total score at the end of treatment. The primary comparison is its change in MDS-NMS total score during the RCT treatment period (days 29-113) versus the change in MDS-NMS total score during the OLE treatment period 1 (days 113-197). This analysis of the primary comparison will only utilize the passive-active treatment group. The analysis will utilize data obtained during the RCT as well as data obtained from the OLE baseline and the twelve weeks of the OLE in which the participants will have been given the intervention.

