7.8.4.1. Combined measure of MDS-UPDRS Parts I, II, and III (sum score)

This endpoint will evaluate the change in the combined measure of MDS-UPDRS Parts I, II and III. The combined measure of MDS-UPDRS Parts I, II, III will be calculated, inclusive of imputation, as described in SAP v6.0 for RCT Study (Appendix 1). For the passive-active group, the change from corresponding baseline to end of treatment

period will be evaluated using a MMRM model similar to the one described for the primary analysis. Treatment differences will be assessed based on the least-squares mean change scores between the passive and active treatments. Changes meeting or exceeding the previously established MCID for this measure (-6.7 points for clinical improvement)⁸ will be considered clinically meaningful.

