7.12. ADDITIONAL SUPPORTING ANALYSES

7.12.1.1. Supportive analysis to further explore clinical significance

Although the structure and methodology for data collection of the MDS-NMS allows for interpretation of the statistically significant changes to be interpreted as inherently clinically meaningful, the scale is relatively new and not well known. As such, to support future clinical adoption by referring physicians, a supplementary analysis is planned as part of the procedures specified in the Statistical Analysis Plan for SNS-PD-002 to establish the MCID for the MDS-NMS. The MCID value identified in the analysis for SNS-PD-002 will define the MCID for analysis in these supporting analyses.

To support the clinical significance of the primary endpoint, the responder rate (i.e., percentage that demonstrate change scores during the first treatment period of the OLE \geq the MCID) in the passive-active treatment group will be reported. Additionally, a McNemar's test will be employed to determine if the responder rate is statistically significantly greater after 12 weeks of tvCVS treatment during the OLE than was the responder rate for this group after 12 weeks of passive treatment during the RCT. The required percentage of participants during the OLE tvCVS that demonstrate a change exceeding the MCID to be statistically significant will be a function of the percentage of participants in the passive-active treatment group that demonstrate a change exceeding the MCID after passive treatment during the RCT. This relationship is depicted in Figure 2. Because the power of this binomial comparison will be reduced under conditions where there is a high responder rate of passive treatment participants during the RCT, if 36% or more of the RCT passive treatment group exceeds the MCID (a condition that would require > 60% responder rate in the active group), the clinical significance for the primary outcome measure will be established by verifying that the

mean difference between responses to the passive treatment RCT and the tvCVS treatment in the OLE exceeds the change equivalent to the MCID.

Effect of Percent in Placebo Group Exceeding MCID

Figure 1: Effect of Percent in Passive (i.e., aka placebo or inactive) Group Exceeding MCID.

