Once the MCID is determined, it can be used to calculate the percentage of cases that exceed that value for each of the two treatment arms (i.e., responder rates). To further support clinical adoption, a supporting Fisher's exact test analysis will be employed to determine if the responder rate for active treatment participants is statistically significantly greater than the response rate for passive treatment participants. For statistical significance, the required percentage of participants in the intervention group that demonstrate a change exceeding the MCID will be a function of the percentage of participants in the passive treatment group that demonstrate a change exceeding the MCID. This relationship is depicted in Figure 3. Because the power of this binomial comparison will be reduced under conditions where there is a high rate of passive treatment participants that exceed the MCID, if 36% or more of the passive treatment arm exceeds the MCID (a condition that would require > 60% responder rate in the active arm), clinical significance for the primary outcome measure will instead be further supported by verifying that the mean/median difference between the two treatment arms exceeds the change equivalent to the MCID.

[figure not shown]

Figure 3: Effect of Percent in Passive Group Exceeding MCID on the Required Percent of Active Group Needing to Exceed MCID to demonstrate statistical significance using binomial comparison.

Additional analyses of the primary endpoint measure to support clinical adoption will include the following:

• The percent change of scores (normalized to the average baseline)

The percent change of scores is calculated as the mean change score divided by the mean baseline value multiplied by 100.

• The percentage of participants who improved by 1 MCID or more (i.e., change from baseline in MDS-NMS Total Score at Day 113 ≥ MCID calculated on an individual level). Participants who do not meet this criterion are non-responders.

The proportion of participants whose change from baseline to Day 113 in NMS-MDS total score met or exceeded the MCID will be summarized by treatment group.

• Effect Sizes

Effect size will be calculated in two ways:

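### The OLE SAP's MCID test compares the active change alone with the MCID, although its stated aim is the active-minus-passive difference

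*SAP*

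**What the plan says.** OLE SAP section 7.8.2.2.1 (Supportive Analysis: Clinical Significance) gives an aim and then a method.

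- **Aim:** to find out "whether the difference in the change scores between the active treatment in the OLE and the passive treatment during the RCT exceeds the MCID" derived from the RCT data.
- **Method:** the test uses the MMRM of RCT SAP section 7.7, "comparing the least-squares mean change of the active treatment (as estimated by the model) to the point estimate of the MCID" obtained in the RCT.

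Other sections work on a difference:

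- OLE SAP 7.8.2 and 7.8.2.1 define the primary comparison within the passive-active group as RCT-period change against OLE-period change.
- OLE SAP 7.8.4.1, for the combined MDS-UPDRS score: "Treatment differences will be assessed based on the least-squares mean change scores between the passive and active treatments". Sections 7.8.4.2, 7.8.4.4 and 7.8.4.5 set a mean difference against the MCID of the scale concerned.
- OLE SAP 7.12.1.1 plans a McNemar comparison of responder rates. It then says that, "if 36% or more of the RCT passive treatment group exceeds the MCID", clinical significance rests on whether the "mean difference between responses to the passive treatment RCT and the tvCVS treatment in the OLE exceeds the change equivalent to the MCID".
- RCT SAP 7.7.1.3 has the parallel check for the randomized comparison: "verifying that the mean/median difference between the two treatment arms exceeds the change equivalent to the MCID".

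The OLE baseline is the RCT end-of-treatment value (OLE SAP 7.4). The MCID will be estimated from RCT data with both arms pooled (RCT SAP 7.7.1.3). Until then the SAP works with a planning range of 32.7 to 35.4 points (RCT SAP section 4).

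**The concern.** The method does not answer the question that the aim poses. The aim is a controlled contrast between two periods in the same participants. The method is an uncontrolled change within one period. Nothing in the SAP says that the active LS mean is already net of the passive change, and where the plan means a contrast elsewhere it says so. A programmer who follows the method sentence literally will report the active change alone.

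The first OLE treatment period is single-arm and open-label, and Protocol section 6.1 has participants told that the OLE offers the treatment shown to be most effective. Some non-specific response from expectation, time or open-label use is therefore plausible, and the written rule removes none of it. OLE SAP 2.1 says that the results are meant to support reimbursement and clinical adoption, where a statement that the MCID was exceeded carries weight. The method also takes the MCID as a fixed number, although it will be estimated in the preceding trial.

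**Working it through.** **The plan's own figure.** No operating characteristic is stated for this MCID test. The nearest figure is the OLE power in OLE SAP section 4: above 98% for a paired t-test with n = 74, difference 2.64, SD 5.32 and alpha 0.05. It reproduces, at 98.8% two-sided and 99.5% one-sided by the noncentral t. It concerns MDS-UPDRS Part I and neither supports nor weakens this point.

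**Notation.** Improvement is negative. A is the mean active change in the OLE, P the mean passive change in the RCT, and M the size of the MCID.

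- Rule as written: -A ≥ M.
- Rule as aimed: -(A - P) ≥ M, that is, A ≤ P - M.

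The two thresholds for A differ by exactly P. An active change that just passes the written rule (A = -M) implies a difference of A - P = -M - P, which is a share 1 + P/M of the MCID.

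**Inputs.** M = 32.7 and 35.4 are the ends of the planning range. The documents give no value for P, so a range is assumed.

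| Assumed P | A - P when A = -32.7 | Share of MCID, M = 32.7 | A needed under the aim, M = 32.7 | Share of MCID, M = 35.4 |
|---|---|---|---|---|
| +10 | -42.7 | 131% | -22.7 | 128% |
| 0 | -32.7 | 100% | -32.7 | 100% |
| -5 | -27.7 | 85% | -37.7 | 86% |
| -10 | -22.7 | 69% | -42.7 | 72% |
| -15 | -17.7 | 54% | -47.7 | 58% |
| -20 | -12.7 | 39% | -52.7 | 44% |
| -30 | -2.7 | 8% | -62.7 | 15% |

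**If the MCID comes out smaller.** RCT SAP 7.7.1.3 falls back on 0.3 times the baseline SD when both anchor correlations are below 0.5. With the SDs in RCT SAP section 4 as proxies, that is 0.3 × 65.87 = 19.8 to 0.3 × 70.8 = 21.2. The gap in points is still P, but it is a larger part of the MCID. At P = -10 the share is 49% to 53% (1 - 10/19.8 to 1 - 10/21.2), and at P = -15 it is 24% to 29%.

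**How often the two rules would disagree (illustration).** Take n = 74, M = 32.7, true P = -15 and true A = -35, so the true difference of -20 is below the MCID. Assume an SD of change of 50 to 70.8 and a within-person correlation ρ of 0 to 0.5.

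- Active alone: SE = SD/√74 = 5.81 to 8.23. The probability that the estimate reaches 32.7 is Φ((35 - 32.7)/SE) = 0.65 to 0.61.
- Difference: SE = SD·√(2(1 - ρ))/√74 = 5.81 (SD 50, ρ = 0.5) to 11.64 (SD 70.8, ρ = 0). The probability is Φ((20 - 32.7)/SE) = 0.01 to 0.14.

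With the same true difference of -20 but P = +10 and A = -10, the active-alone probability falls to between 0.000 and 0.003, while the difference keeps 0.01 to 0.14. The direction depends on P.

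**The case against.** **A stronger reading is tempting:** that the RCT passive response is counted inside the active change as device benefit. The documents do not support it. OLE change starts from the RCT end-of-treatment value, so the passive change has already happened and lies outside A. If the passive response is a lasting shift complete by day 113, A is already measured from the shifted level, and subtracting P could over-correct. What the written rule leaves unsubtracted is new non-specific response during the OLE, for which the passive period stands in. Its size is unknown. This limits the mechanism. It does not remove the mismatch, because subtracting the passive-period change is what the stated aim and the primary comparison do.

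**Direction.** A reader might also infer that the rule always favours the device. It does so only if passive participants improve.

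**Partial cover elsewhere.** Section 7.12.1.1 compares responder rates between the periods, and uses the mean difference when passive response is high. That stands, but the mean-difference check is conditional on 36% or more passive responders. Below that, the only mean-versus-MCID comparison written for the primary outcome in the OLE is the uncontrolled one.

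**The MCID is a within-patient threshold.** It is built to separate minimally improved from unchanged patients, so setting a within-period change against it can be defended. But that is not the aim stated in 7.8.2.2.1, and the responder analysis in 7.12.1.1 already serves the within-patient question.

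**Consequence.** The analysis is labelled supportive and lies outside the testing hierarchy. OLE SAP 7.8.2.2 ties success to the statistical test of the period-to-period difference. That is correct and limits the severity.

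**Conclusion.** The contradiction is certain from the text: two consecutive sentences of OLE SAP 7.8.2.2.1 define different quantities, and the operative one does not answer the stated question. The rules differ by P. For an assumed passive improvement of 10 to 20 points and an MCID of 32.7 to 35.4, an active change that just passes represents 39% to 72% of the MCID as a difference. These sizes rest on assumed values of P and on planning MCIDs; the final MCID will come from the RCT. The probabilities rest further on an assumed SD of change and within-person correlation.

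The point reaches only the supportive claim that the MCID was exceeded. A reader might infer that the OLE primary test is compromised, but that test is specified as a contrast between the periods and is unaffected. The text should be corrected before analysis.

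**What to change.** In section 7.8.2.2.1, replace the comparison of the active LS-mean change with the model's LS-mean contrast, active OLE change minus passive RCT change, and set it with its confidence interval against the MCID. State the confidence level, and whether the estimate or the interval limit must exceed the MCID. This agrees with the stated aim and with section 7.12.1.1. Show the active change alone descriptively. Add that the MCID is itself an estimate from the RCT; an interval for the contrast alone does not carry that uncertainty.

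Restating the aim as a within-period change would also remove the contradiction, but the result would be an uncontrolled claim from an open-label period and would still differ from 7.12.1.1.

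The cost is a sentence or two in the SAP and no new data, since the same model gives the contrast. The downside for the sponsor is that the result may be less favourable if passive participants improved during the RCT.

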7.8.4. Secondary Endpoints

Multiplicity of study endpoints will be adjusted for using a hierarchical strategy whereby endpoints in the study are only considered to be statistically significant if both of the following are true: 1) p < 0.05 AND 2) the preceding endpoint was found to be statistically significant at the significance level $\alpha = 0.05$. More specifically, the hierarchical order for evaluation of efficacy endpoints is the following:

- 1. MDS-NMS Total Score (primary endpoint);
- 2. Combined measure of MDS-UPDRS Parts I, II, and III (sum score)
- 3. MDS-UPDRS Part II (secondary endpoint);
- 4. Overall CGI-I (secondary endpoint);
- 5. MDS-UPDRS Part III (secondary endpoint);
- 6. PDQ-39SI (secondary endpoint).

Note that all secondary endpoints have an *a priori* direction, thus, one-tailed tests will be utilized for analyses.

Secondary endpoint analysis will be conducted using the passive-active treatment group for the primary comparison of interest.

Analyses of the secondary endpoints will be conducted in a manner consistent with the primary endpoint except where noted.

7.8.4.1. Combined measure of MDS-UPDRS Parts I, II, and III (sum score)

This endpoint will evaluate the change in the combined measure of MDS-UPDRS Parts I, II and III. The combined measure of MDS-UPDRS Parts I, II, III will be calculated, inclusive of imputation, as described in SAP v6.0 for RCT Study (Appendix 1). For the passive-active group, the change from corresponding baseline to end of treatment

period will be evaluated using a MMRM model similar to the one described for the primary analysis. Treatment differences will be assessed based on the least-squares mean change scores between the passive and active treatments. Changes meeting or exceeding the previously established MCID for this measure (-6.7 points for clinical improvement)⁸ will be considered clinically meaningful.

7.8.4.2. MDS-UPDRS Part II

This endpoint will evaluate the change in MDS-UPDRS Part II score to provide a measure of activities of daily living related to motor function. The total score for MDS-UPDRS Part II will be calculated as described in the SAP v6.0 for RCT Study (Appendix 1). For the passive-active group, the change from corresponding baseline to end of treatment period will be evaluated using a MMRM model similar to the one described for the primary analysis. Treatment differences will be assessed based on the least-squares mean change scores between the passive and active treatments. Changes will be considered to be clinically meaningful if the mean difference exceeds the previously established MCID (-3.05 for clinical improvement)⁹.

7.8.4.3. Overall CGI-I

The CGI-I provides a clinician's determination of overall change as it relates to all aspects of Parkinson's disease. For ease of interpretation, the CGI-I score will be converted by the following formula: Converted CGI-I = 4 - CGI-I. Thus a 0 corresponds to no change, higher magnitude positive values correspond to greater improvements and higher magnitude negative scores correspond to increased worsening. For the passive-active group, treatment differences will be modeled utilizing the MMRM with no effect for visit as described previously. The effect of the device in the OLE will be considered clinically significant if converted CGI-I scores after active tvCVS during the OLE are statistically significantly greater to those after passive treatment in the RCT.

